Specific Aim 1a. To evaluate the feasibility and acceptability of a 9-month TRF intervention compared to a standard dietary weight loss intervention (i.e. RCD). Feasibility of enrollment and retention, and acceptability of the intervention will be assessed in adults with obesity meeting inclusion/exclusion criteria proposed for the future large-scale trial. We will assess adherence to the weight loss programs, as measured objectively with a novel smartphone application and verified with CGM data, and subjectively with the use of questionnaires. We expect adherence to the RCD+TRF intervention will be similar to the RCD group, suggesting acceptability for a future large-scale trial. If we find differences in adherence between programs, the data will be used to optimize the RCD+TRF program prior to the future large-scale trial.

Specific Aim 1b. To assess the efficacy of RCD+TRF compared to RCD alone in producing weight loss at 12 weeks and reducing the risk of weight regain after 6 months of follow-up. Although the number of subjects included in this pilot study does not provide sufficient statistical power to detect differences in weight loss between groups, the data obtained will provide estimates of variability and effect size to assist with power and sample size calculations for the future large-scale trial

Exploratory Aim. To explore potential mechanisms contributing to any observed differences between groups we will evaluate (A) objective measures of free-living behavior (energy intake, physical activity, and sedentary behavior) and (B) objective measures of glucose variability, sleep and energy metabolism Preliminary data on free-living behaviors and

in-laboratory measures of sleep and energy metabolism will allow us to further optimize a future trial and probe mechanisms to explain any weight loss differences between groups.

II. Background and Significance:

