Intervention Acceptability: Satisfaction with both the standard RCD and RCD+TRF program intervention will be assessed at week 12 and month 9 with a questionnaire that asks participants to rate on a 1-10 Likert scale how satisfied they were with specific domains of the intervention. The major domains that will be assessed are satisfaction with: 1) ability to adhere to caloric restriction and time restriction (for RCD+TRF group), 2) content of the dietary support curriculum, 3) content of the exercise support curriculum, 4) group meeting frequency and structure, and 5) weight loss achieved to date. Participants will also be asked in open-ended fashion to provide feedback on each domain of the intervention. We will also assess intervention acceptability by comparing the frequency of protocol related AE's, requirement for protocol modification, and attrition between groups.

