In addition, at the end of the intervention, participants in both the TRF and RCD groups (n=6-8 per group) will be asked to participate in focus groups led by [name], a licensed clinical health psychologist with experience developing heath focused behavioral interventions and conducting focus group research. The participants will be required to fill out an additional consent form. If the study team is unable to meet with them in person to obtain consent, then a virtual consent will take place via ZOOM. The goal of the focus groups will be to obtain more specific information about their perceptions of, and experiences with, the intervention. Participants will specifically be asked to discuss, via open-ended inquiry and discussion: 1) aspects of the intervention itself that were difficult or relatively easy to follow; 2) barriers that limited their adherence or satisfaction; 3) beneficial aspects of the intervention; 4) factors that facilitated their ability to adhere to the intervention; 5) aspects that they would change and their recommended changes. To obtain a more complete understanding of the participants' experiences, extensive efforts will be made to include individuals who were non-adherent or dropped out of the interventions. A research assistant will attend the focus groups to act as a scribe, and the sessions will also be recorded using an audio recording device which will be later used to transcribe the entire session. Once the recording has been transcribed, the audio recording will be deleted. Data in response to the open-ended queries will be analyzed by the focus group leader using primarily inductive procedures, searching for themes that could inform intervention refinement in advance of a larger clinical trial. The focus groups will last 60-90 minutes and will be conducted at the Anschutz Health and Wellness Center.

In case of situations in which in-person classes cannot be held (i.e., due to concern for transmission of disease during the COVID-19 global pandemic), meetings will be held virtually via Zoom. Zoom is a HIPAA compliant web and video conferencing platform. All participants will be provided with a link to join the meeting and instructions regarding optimal conditions in which to join the meeting (i.e., a quiet location with minimal distractions and ability to devote full attention to the meeting).

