Due to the COVID-19 pandemic, we are unable to carry out week 12 measures as described above. Instead, the study team will drop off the accelerometer and wrist actigraph to participant's homes. The packet of devices will be left on the participant's doorstep to eliminate person to person contact. Proper PPE will be worn by the study team during the drop-off and pick-up time including gloves and masks. The participants will be asked to wait a few days before wearing the devices and encouraged to wipe each device down before placing it back in the packet for pick-up. Once the participants have worn the device for 7 consecutive days, the study team will pick up the devices from the doorstep and wipe down the packet with a disinfecting wipe. The devices will not be handled by the study team for at least 1 week post pick-up. The devices will be handled as follows:

- The study team will wear gloves and a mask any time they are handling devices
- Devices will be disinfected with a Cavi-wipe before being placed in the individual device packets
- Each device will be placed in its own sanitized plastic bag before being placed in the device packet
- Devices will be given to the entire cohort on one date, so that there will be no sharing of devices between participants
- No study team member will handle devices if they are exhibiting symptoms of COVID-19 or have been exposed in the last 14 days.

These measures will be put into place so long as the orders from campus, local, state, or federal government are such that the study measures cannot be carried out as originally planned. The study team will resume normal visit procedures once it is safe and permitted to do so.

We will still collect all non-contact outcomes such as the appetite recording (VAS), and the 7 days of food logging via Google voice. In addition to these measures, for the cohort participating in the weight loss intervention during the COVID-19 pandemic only, we will administer a questionnaire specific to COVID-19 (changes in work, levels of motivation, ability to adhere to the diet, etc) as well as the Perceived Stress Scale, a validated psychological instrument for measuring the perception of stress. CTRC measures such as the DXA, blood panel, and resting metabolic rate will not be collected under these circumstances.

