E. Potential Scientific Problems:

Adherence to the TRF protocol: This will be the first study to our knowledge that will assess the feasibility of using TRF in the context of a reduced calorie diet for weight loss. We will objectively measure compliance to the protocol at baseline and 12 weeks using CGM and photographic time-stamped food logs but will otherwise not know whether subjects randomized to the TRF group were compliant to the protocol. To limit the extent of possible non-compliance to the TRF arm we decided on a shorter intervention for our first study. We are also using a high intensity behavioral support program that will meet weekly to discuss dealing with hunger/cravings or other challenges that might be associated with TRF. We will also ask participants to keep a log documenting daily feeding duration (first and last energy intake events) during all intervention weeks.

F. Data Analysis Plan:

Sample Size Justification:. We will aim to recruit 60 participants in two cohorts.. The sample size was determined for the primary outcome, change in body weight (kg) at 12 weeks. Assuming 20% attrition, we will be left with n=48, or n=24 subjects per group. To justify the sample size, we computed the detectable difference that we have 80% power for based on existing preliminary and published data. We will assume an alpha=0.05 and use two-sample t-tests. We assumed that the RCD group will have similar weight loss as has been shown previously with the standard Colorado Weigh curriculum, in which the mean \pm standard deviation (SD) weight loss using an intent-to-treat analysis at 12 weeks is -4.1 \pm 3.7kg⁵⁷. There are no prior relevant data for 12-week weight loss using TRF in the context of a weight loss intervention. However, prior data from the Gill and Panda study²⁶ of time restricted feeding without a weight loss intervention showed a mean weight loss at 16 weeks of -3.3 kg with a SD=3.4 kg. Given that we are combining the RCD and TRF treatments, the standard deviation is likely to be between 3.4kg and the sum of the variation of the RCD and

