time restricted studies (SD of the sum = $\sqrt{3.7^2 + 3.4^2} = 5.0 \text{ kg}$). In our calculation, we assumed for the time restricted treatment group (RCD+TRF) a SD in-between the above lower and upper bounds of SD at 4.2kg. With these SD's, we have 80% power to detect a difference in mean weight loss between the two treatment groups of 3.5kg. This is slightly larger than the Gill and Panda study, but well within the range of the confidence interval of their result. In addition, this calculation is quite conservative. We will have power of 80% to detect an even smaller difference in weight loss between the groups, because in the final analysis we will adjust for baseline weight, which reduces the SD's in each of the groups and allows us to have power to detect smaller differences. The intervention will be modified if we are unable to recruit 30 participants, retain >70% of participants, or perform outcome measures within a 2-week window of the indicated time points in >90% of participants.

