The importance of understanding mechanisms underlying the tendency for obese people to regain weight after they have lost weight cannot be overstated given the current epidemic of overweight and obesity and the prevalence of chronic diseases in the U.S. and other developed countries worldwide related to the clinical problem of obesity. Obesity is a major risk factor for many clinical conditions including type 2 diabetes, cardiovascular diseases, heart disease, hypertension, cancer, arthritis and can lead to premature death and disability. Another major problem posed by the overweight/obesity pandemic is the concomitant rise of a cluster of life-shortening risk factors referred to as metabolic syndrome. The metabolic syndrome represents a constellation of metabolic features including insulin-resistance, dyslipidemia, hypertension, and non-alcoholic fatty liver disease. While not regarded as a chronic disease, the metabolic syndrome increases risk of developing type 2 diabetes and cardiovascular disease. Altogether 133 million Americans - almost 1 out of every 2 adults - has at least one chronic illness, which results in 7 out 10 deaths every year. Medical costs associated with obesity were estimated at \$147 billion; the medical costs for people who are obese were \$1,429 higher than those of normal weight. In total, 75% of the US health care is spent on people with chronic conditions. Many people are able to lose weight but weight regain is almost universal following weight loss and is the biggest impediment to addressing the obesity epidemic. In this context, the proposed study has strong scientific, clinical, public-health and economic relevance.

Future Directions. Data will be used to optimize the RCD+TRF program delivery and to inform the planning of a grant proposal for a large-scale interventional trial to test the efficacy of RCD+TRF as compared to standard RCD with respect to body weight, fat mass, PA, metabolic outcomes, glucose variability and sleep. Further directions include the evaluation of specific time periods for restriction (e.g., earlier vs later during the day), and shorter vs longer duration of restriction. The role of baseline eating behaviors, especially chronotype, can be explored in future studies. Additionally, it would be of interest to evaluate the use of TRF after weight loss, during the weight maintenance period or in individuals with metabolic disease (i.e. T2DM, hyperlipidemia).

H. References:

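### Does the overall >70% retention trigger, left unadapted to the COVID closure, undermine the feasibility assessment?

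*Combined protocol and SAP*

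**What the plan says.** The rule closes the Sample Size Justification in Section IV.F. It has three parts: "The intervention will be modified if we are unable to recruit 30 participants, retain >70% of participants", or fails to "perform outcome measures within a 2-week window of the indicated time points in >90% of participants". It names no arm, gives no denominator and does not list which measures count. The planning figure for retention stands in the same section: "Assuming 20% attrition, we will be left with n=48, or n=24 subjects per group".

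Other sections bear on the same question:

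- Section IV.C, Intervention Acceptability, compares between arms the frequency of protocol-related adverse events, "requirement for protocol modification, and attrition between groups". It gives no cut-off and names no test.
- Specific Aim 1a says that if adherence differs between programmes, "the data will be used to optimize the RCD+TRF program prior to the future large-scale trial".
- The focus groups in Section IV.C make a point of including people who dropped out or did not adhere, "searching for themes that could inform intervention refinement in advance of a larger clinical trial".
- Section IV.G, Future Directions, sets no condition: "Data will be used to optimize the RCD+TRF program delivery".
- Section IV.C, COVID-19 Post Intervention Changes, states that "CTRC measures such as the DXA, blood panel, and resting metabolic rate will not be collected under these circumstances". Accelerometry, actigraphy, appetite scales and food logging continue.
- Section IV.C, Post-intervention assessments, allows 3 weeks after the 12-week programme for the 7-day recordings, where the rule speaks of a 2-week window.

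**The concern.** Feasibility is a primary outcome, and the hypothesis is that RCD+TRF will be about as feasible and acceptable as RCD. RCD uses an established curriculum; the RCD+TRF curriculum is new. If one arm struggles, it is more likely to be RCD+TRF, and a pooled criterion lets the other arm make up the shortfall. The only numeric trigger could then stay silent while the experimental programme lost close to half its participants.

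The opposite failure looks possible too. DXA, blood tests and resting metabolic rate supply listed secondary outcomes. If their suspension counts against the >90% criterion, the rule could fire because a site closed and not because the intervention failed. The text does not settle this, so the same data might be called a pass or a fail afterwards.

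**Working it through.** **Inputs.** From the plan: 60 participants, 1:1 allocation (30 per arm), 20% attrition, thresholds >70% and >90%. Assumed: every true retention rate other than the plan's 80%, and Fisher's exact test at 0.05 for the attrition comparison.

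**The plan's own figure.** 60 × (1 − 0.20) = 48, or 24 per arm. This reproduces.

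**What the pooled criterion permits.** 0.70 × 60 = 42, so >70% means at least 43 retained.

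- 27 + 16 = 43: RCD+TRF at 16/30 = 53%. Fisher two-sided p = 0.003.
- 25 + 18 = 43: RCD+TRF at 18/30 = 60%. Fisher p = 0.084.

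**How often it would pass.** With X ~ Bin(30, p₁) retained in RCD and Y ~ Bin(30, p₂) in RCD+TRF, the pooled rule passes when X + Y ≥ 43. The same threshold within RCD+TRF needs Y ≥ 22, since 0.70 × 30 = 21.

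| True RCD / RCD+TRF | Pooled passes | RCD+TRF alone passes | Pooled passes, RCD+TRF ≤ 21, Fisher p ≥ 0.05 |
|---|---|---|---|
| 90% / 55% | 0.628 | 0.031 | 0.105 |
| 90% / 60% | 0.789 | 0.094 | 0.176 |
| 85% / 55% | 0.447 | 0.031 | 0.157 |
| 85% / 60% | 0.625 | 0.094 | 0.258 |
| 80% / 55% | 0.287 | 0.031 | 0.148 |
| 80% / 60% | 0.449 | 0.094 | 0.244 |

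The last column is the gap that remains once the planned attrition comparison is counted: 11% to 26%, under assumed arm differences of 20 to 35 percentage points.

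**What an added arm-level criterion would cost.** Probability that the retention criterion is met when both arms truly retain more than 70%:

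| True retention, both arms | Pooled only | Pooled and RCD+TRF ≥ 22/30 | False triggers |
|---|---|---|---|
| 80% | 0.957 | 0.858 | 4% → 14% |
| 75% | 0.775 | 0.614 | 23% → 39% |

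A looser arm threshold of 20/30 (67%, below the plan's own figure) keeps 0.944 at 80%. On its own, though, it would pass an RCD+TRF arm with true retention of 55% or 60% with probability 0.135 or 0.291. A cut-off at this size is noisy in any case: 21/30 has an exact 95% interval of 51% to 85%.

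**Measurement criterion.** If the denominator were everyone enrolled, the plan's own attrition would give 48/60 = 80% and fail >90% with no closure at all. The workable reading is therefore participants still enrolled. On that reading:

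- 48 retained: 0.90 × 48 = 43.2, so 44 are needed and 4 may be missing.
- 43 retained: 39 needed, 4 may be missing.
- 60 retained: 55 needed, 5 may be missing.

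A closure affecting a handful of people would breach the criterion, but only if suspended measures count. The number affected is not stated.

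**Window.** Starting within 2 weeks and recording for 7 days ends within 14 + 7 = 21 days, which is the 3 weeks allowed. The two statements agree if the 2-week window refers to the start of recording.

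**The case for a change.** The strongest argument for amending is that a between-group comparison does not replace a threshold. It asks whether the arms differ, not whether RCD+TRF retention is good enough. At 25/30 against 18/30 a test would probably be called inconclusive and the rule would be silent, so whether 60% retention calls for modification is left to judgement. The other routes to refinement permit a change but never require one. The protocol was updated for COVID-19 in several places and this sentence was not. The amendment would be one sentence and need no new data.

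The facts in this stand: no section supplies an arm-level cut-off or a COVID exception. The inference is weaker. A pilot does not need a significant test to act on 60% against 83%; the planned comparison shows both figures. Section IV.G commits to improving RCD+TRF whether or not the rule fires. The extreme case that makes the concern striking, 53% against 90%, is the one the attrition comparison would expose most clearly.

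Timing also counts against a new cut-off. The Baseline Assessments section records that meal-log collection in Cohorts 1 and 2 was finished by January 2020, and this version is dated October 2020. Participants and group leaders know the allocation because the arms meet separately. A threshold chosen now could be influenced by attrition already seen.

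**Conclusion.** No change is called for. The retention trigger is pooled and could stay silent when RCD+TRF retention is poor: at an assumed 90% and 55% it passes with probability 0.63, against 0.03 for the RCD+TRF arm alone. But the rule's only stated consequence is that the intervention is modified, and the plan already compares attrition by arm and undertakes to refine RCD+TRF. No estimate or test depends on the rule, and the feasibility conclusion stays sound because retention by arm will be visible. Choosing an overall or a per-arm threshold at 30 per arm is a fair trade-off between missed and false alarms, and changing it after data have accrued brings a cost of its own.

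The remaining points are details that an analyst would fill sensibly: timeliness among those still enrolled, suspended measures treated as no longer due for the affected participants, and the 2-week window taken as the start of recording. This rests on retention actually being reported by arm, as the acceptability section implies, and on closure-related gaps being described as such. All retention rates other than 80% are assumptions.

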El and meal timing will be measured using photographic food records by utilizing the camera function of participants' smartphones to take a picture of the food or beverage. Participants will be provided with detailed instructions regarding methods of taking food photographs, as outlined by the CTRC Nutrition Core. After taking the photographs, participants will text photographs directly to either a Meallogger account or a Google Voice account (note: an amendment was submitted in 1/2020 to switch to Google Voice after data collection using Meallogger in Cohorts 1 and 2 were already completed.). Subjects will be asked to record every intake event for 7 continuous days. The data from this 7-day recording period will be used to assess timing of energy intake in both groups, and adherence to time restriction in those patients in the RCD+TRF group. In addition, this information will be compared with data from continuous glucose monitoring to determine whether glucose excursions exist in the absence of recorded food intake events. Based on published data⁴⁰ showing that mean post-prandial glucose excursions in patients with normal glucose tolerance are ~40.5 mg/dL, this threshold will be used to indicate an episode of food intake. El will be estimated using the food images collected during the last 3 days of the 7 day recording period by staff in the CTRC Nutrition Core, as previously described^{41,42}.

Glucose variability: Free-living plasma glucose levels will be measured with a glucose monitoring

system (FreeStyle LibrePro, Chicago, IL) for 7 continuous days coinciding with the cell phone-based meal tracking described above. The device consists of a sensor applied to the back of the patient's upper arm that measures glucose in interstitial fluid every 15 minutes.

Patterns of PA and Sedentary Behavior: The activPAL3 micro (PALTechnologies, Glasgow, Scotland) will be used to estimate time spent in moderate-to-vigorous PA (MVPA), light activity, and sedentary behavior over a 7-day period at baseline. The activPAL3 micro uses accelerometer-derived information about thigh position to estimate time spent in different body positions. The time-stamped "event" data file from the activPAL software will be used to determine time spent sitting, standing, and stepping per day.

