Adherence: Adherence to the prescribed study diet will be objectively assessed through review of meal logs collected with the MealLogger app and Google Voice account as described above, as well as through evaluation of glucose excursions in comparison with the meal logs in order to determine if glucose excursions exist in absence of recorded food intake. In addition, adherence will be assessed subjectively as described above through the use of questionnaires using Likert scales to address ability to adhere to the study diet.

Post-intervention assessments. Within 3 weeks following the initial 12-week weight loss intervention all participants will complete 7 days of free-living EI recording (cell phone app), PA recording (accelerometers), sleep recording (wrist actigraph), appetite recording (VAS), and glucose monitoring (CGM) as described above for the baseline assessments. Participants will also have repeat assessments of HgbA1c, lipid panel, resting metabolic rate and body composition (DXA) during an outpatient CTRC visit. Participants will also repeat questionnaires as described above: adherence to the dietary intervention, QOL (RAND-36), mood state (POMS-2), eating behaviors (TFEQ), and sleep questionnaires (Berlin Questionnaire, Epworth Sleepiness Scale, Pittsburgh Sleep Quality Index, and Morningness -Eveningness Questionnaire). Participants completing the optional in-laboratory room calorimeter and objective sleep measurements at baseline will be asked to complete follow-up measurements. The follow-up measurements of sleep and nocturnal energy metabolism can be completed on any evening starting at week 10 of the intervention not to exceed 4 weeks following completion of the intervention. The only exception is that the inpatient visit cannot occur during the 7 days of free-living EI, PA, and glucose monitoring.

COVID-19 Post Intervention Changes

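### Can a pilot that runs exactly as planned fail its own 90% on-time measurement threshold?

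*Combined protocol and SAP*

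**What the plan says.** Section IV.F, Sample Size Justification, closes with three conditions under which the intervention is to be modified: the team cannot recruit 30 participants, retain more than 70%, "or perform outcome measures within a 2-week window of the indicated time points in >90% of participants". It does not define the denominator, list the measures or time points that count, or say whether the window applies to the start or the end of a multi-day recording. The same paragraph plans for dropout: "Assuming 20% attrition, we will be left with n=48, or n=24 subjects per group".

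Section IV.C, Post-intervention assessments, sets its own limits. For the free-living recordings: "Within 3 weeks following the initial 12-week weight loss intervention all participants will complete 7 days of free-living" recording. For the optional overnight sleep and metabolism measures, the follow-up "can be completed on any evening starting at week 10 of the intervention not to exceed 4 weeks following completion of the intervention". The clinic measures (HbA1c, lipids, resting metabolic rate, DXA) are given no separate limit there.

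Section IV.C, COVID-19 Post Intervention Changes, adds: "CTRC measures such as the DXA, blood panel, and resting metabolic rate will not be collected under these circumstances".

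**The concern.** Feasibility is a primary outcome in Section IV.A, and the three thresholds are the plan's only numeric feasibility rules. Such a rule should give one answer for one dataset, and three features suggest that this one may not.

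- **Denominator.** The 70% and 90% figures apply to the same undefined group. If that group is everyone enrolled, the plan's own 20% attrition already rules out exceeding 90%.
- **Window.** A recording completed in the third week complies with Section IV.C but could count as late under Section IV.F. The same applies to an overnight stay in the third or fourth week.
- **COVID-19.** Measures that the plan itself says will not be taken could count as misses. A whole group is exposed to this, because the protocol describes special arrangements "for the cohort participating in the weight loss intervention during the COVID-19 pandemic only".

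If these readings were left open, the choice between modifying and proceeding could be made after the results are known.

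**Working it through.** **Inputs.** From Section IV.F: 60 enrolled, 20% attrition, thresholds of 70% and 90%, a 2-week window. From Section IV.C: a 3-week limit for the 7-day recordings, a 4-week limit for the optional overnight measures, and about 5 overnight studies per group.

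**1. The plan's own figure.** 60 × (1 − 0.20) = 48, or 24 per group. This reproduces.

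**2. Counts needed.**

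| Rule | Base | Fraction × base | Smallest count that passes |
|---|---|---|---|
| >70% retained | 60 | 42 | 43 |
| >90% on time | 60 enrolled | 54 | 55 |
| >90% on time | 48 retained | 43.2 | 44 |

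**3. Denominator.** With 48 retained and all on time, the score is 48/60 = 80.0% (fail) or 48/48 = 100% (pass). The arithmetic of the apparent conflict is therefore right. On the enrolled base, however, passing requires at least 55 people measured, hence at least 55 still present. The retention rule needs only 43, so it could never be the deciding rule. If each person is retained independently with probability 0.80, the enrolled-base rule passes with probability P(X ≥ 55) = 0.012 for X ~ Binomial(60, 0.80), even with perfect timing. The retention rule passes with probability P(X ≥ 43) = 0.957. A team that budgets for 20% attrition and sets a separate 70% retention floor cannot have meant a rule that its expected attrition defeats about 99 times in 100. The reading that gives both rules a purpose is that retention is judged among those enrolled and timeliness among those still enrolled.

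**4. Retained base.** Four of 48 may be missed. The documents give no on-time rate, so the following rates are assumptions, with X ~ Binomial(48, q):

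| Assumed on-time rate q | P(X ≥ 44) |
|---|---|
| 0.85 | 0.134 |
| 0.90 | 0.469 |
| 0.95 | 0.909 |
| 0.97 | 0.986 |

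This is how a 90% threshold should behave: about even odds when the true rate sits at the threshold, and a clear pass when timing is good.

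**5. Window.** If the 2 weeks governs the start, the latest compliant recording begins on day 14 and ends by day 14 + 7 = 21, which is 3 weeks. The two limits then agree. If the 2 weeks governs completion, days 15 to 21 count as late, and five such recordings give 43/48 = 89.6%, a fail. The conflict exists only on the completion reading, and only for the free-living recordings. Section IV.A places weight and DXA at 12 weeks, and no limit for them elsewhere contradicts 2 weeks.

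**6. Optional overnight measures.** About 5 × 2 = 10 people are planned, and 10/48 = 20.8%. A rule requiring more than 90% of participants cannot be meant to cover a measure planned for about a fifth of them.

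**7. COVID-19.** Five affected people among 48 would cap DXA, blood tests and metabolic rate at 43/48 if uncollected measures counted as misses. The size of the affected cohort is not stated, so the actual cap cannot be computed. The restriction applies to week-12 measures and lapses when normal visits resume.

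**The case for a change.** The strongest case for a change is that the rule is worded as binding and serves a primary outcome, yet the retained denominator and the start-of-recording reading are both inferred. The only analysis population that the plan defines, in the Statistical Analysis paragraph of Section IV.F, is everyone randomized. Late or missing week-12 measures may also cluster, because the COVID-19 section has devices delivered to a whole cohort on one date. One sentence would settle all of this before scoring.

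Part of this stands. The denominator, the start-or-completion rule and the handling of prohibited measures are not written down, and on the completion reading five fully compliant participants could tip the result. The randomized population is a weaker argument, because it is set for the efficacy comparison and is not tied to the feasibility thresholds. The COVID-19 gap is a matter of bookkeeping: any competent feasibility report would separate measures that the site was barred from taking from measures taken late.

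**Conclusion.** No change follows. The plan leaves detail unstated, but it does not contradict itself on the reading that its own sentence supports: timeliness counted among those still enrolled, with recordings started within 2 weeks. On that reading 48 retained and on time scores 100%, and the 3-week completion limit fits. The 80% score needs a denominator that would leave the adjacent retention rule without effect. The third-week conflict needs the completion reading.

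The consequence is small. The rule feeds a judgement about refining the programme before a larger trial, and the plan does not say what modification would follow. It does not enter randomization, the mixed model, the 0.05 level or the sample size. This conclusion assumes that the team reports the denominator and the window it used, and shows measures withheld under COVID-19 restrictions separately. The on-time rates above are illustrative, since the documents give none.
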